Pantothenate kinase-associated neurodegeneration (PKAN) is an inborn error of vitamin B5 metabolism. Children with the classic form of the disease suffer from a progressive neurodegenerative disorder that begins in the first few years of life, characterized by a severe movement disorder, cognitive and neuropsychiatric abnormalities, and pathologic iron accumulation in the basal ganglia of the brain. Children typically lose independent ambulation before age 10 and many die in the first decade of life. Those individuals who have disease onset later in life tend to have less severe manifestations but nonetheless suffer profound disability^[1,2]. Pathologically, the disease shows remarkable regional specificity in the brain, selectively affecting the globus pallidus, with very limited involvement of other regions^[3]. PKAN is an orphan disease, with a prevalence of 1-2 cases per million in the general population^[4], with higher prevalence reported in a few small populations where geographic, socio-economic, cultural or religious factors have resulted in founder mutations^[4,5]. Treatment options are currently limited to symptomatic management: there are no proven disease-modifying agents available.

b. PKAN Patients cannot metabolize vitamin B5 normally to make coenzyme A

PKAN is caused by mutations in the *PANK2* gene, which encodes one of four pantothenate kinase (PANK) enzymes in the human that serve to phosphorylate vitamin B5 in the rate-limiting step in coenzyme A (CoA) metabolism [Figure 1]. CoA is essential for the tri-carboxylic acid cycle, fatty acid oxidation and synthesis, amino acid metabolism and neurotransmitter synthesis, serving more than 9% of mammalian biochemical reactions^[6].

[figure not shown]

Figure 1: Coenzyme A metabolic pathway. Patients with mutations in the *PANK2* gene lack an enzyme to phosphorylate vitamin B5 (pantothenate) in selected regions of the brain in the key regulatory step in the coenzyme A (CoA) biosynthetic pathway. PPAT and DPCK together comprise the bi-functional enzyme CoASY. 4'-phosphopantetheine is a product of intermediary metabolism that is converted by CoASY into CoA.

c. Molecular and functional evidence of the disease is seen in the PANK2 knock-out mouse

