Note that the double-blind phase of this study is not intended to be dose-finding: all doses are predicted to be many-fold below toxicity and all doses are predicted to correct the metabolic defect in PKAN, albeit with slightly differing time courses. The range of doses to be used during the double-blind phase is employed to test our hypotheses regarding the pharmacodynamic profile of an exploratory biomarker, CoASY. The mid-dose of 15mg/m² that will be given to all participants during the open-label phase is based on the minimum effective dose in the mouse and converted to the human equivalent dose using an FDA algorithm and other guidances^[13,14]. The actual single daily dose in mL to be taken by the study participant will be calculated by the research pharmacist based on the participant's body surface area. If a subject has difficulty taking the volume of the single dose, then at the Principal Investigator's discretion the dose may be divided into 2 equal volumes and taken twice a day.

7. Study Population

a. Number of Subjects

We will screen up to 150 individuals with the goal of enrolling 64 participants, to achieve 60 participants completing the double-blind arm of the study as the Primary Cohort. We are conservatively allowing for 4 dropouts (5% loss) based on our experience in one other interventional clinical trial with this clinical population; however, if participant loss is higher than anticipated during the projected 24 month recruitment phase, we will strive to replace all dropouts to maximize our chances of achieving 60 participants completing the study. Once enrollment into the Primary Cohort is met, we will shift to enrolling up to 86 additional participants in the direct to open-label arm (Open-label Cohort).

Classic PKAN participants are defined as those with onset of motor symptoms before age 5 and (if over 10 at enrollment) loss of independent ambulation by age 10. Goal is n=30 classic participants.

Atypical PKAN participants are defined as all other PKAN participants who don't meet classic disease criteria. Goal is n=30 atypical participants.

b. Inclusion and Exclusion Criteria

For inclusion in this trial, subjects must:

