- The subject has a diagnosis of PKAN confirmed by: a) genetic testing confirming 2 pathogenic or likely pathogenic mutations, or (b) typical findings on exam and brain MR imaging with only one pathogenic mutation +/- a second likely pathogenic or Variant Of Uncertain Significance (VOUS) in *PANK2*, or (c) typical findings on exam and brain MR imaging with a single likely pathogenic or VOUS in *PANK2*, or (d) be a symptomatic sibling of a proband subject meeting a, b, or c.
- Be between age 3 months to age 89 years at the time of screening.
- Be able to take the study product by mouth or via gastrostomy tube.
- Be willing and able to complete study procedures / telephone visits / blood draws independently, OR have a caregiver / parent willing and able to assist with these tasks.
- Be enrolled or willing to enroll in the PKANready natural history study (eIRB 10832).
- Be resident in North America for the duration of the trial.

For inclusion in this trial, subjects must NOT:

- Have been exposed to a putative *PANK2* 'bypass' therapeutic agent in the 30 days prior to screening.
- Be concurrently enrolled in another interventional clinical trial.
- Have concurrent medical or other conditions that in the opinion of the investigators are expected to preclude completion of study procedures or confound the assessment of clinical and laboratory measures of safety.

[name], OHSU clinical geneticist, will serve as an independent eligibility reviewer for the study. He will review whether each subject meets the inclusion criteria before they may be consented.

c. Vulnerable Populations

This study will include vulnerable populations as a necessary part of the research. In particular, children will be included because PKAN disproportionately affects children. Those with classic PKAN are affected in the first few years of life and tend to have more severe and rapidly-progressive disease, and it is this sub-population in whom dietary management is ultimately expected to have the greatest impact.

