Similarly, we will check for **treatment response when the placebo group initiates treatment after month 6** by recoding their observations to use month 6 as 0 (baseline). We will use the same regression model but expect $\beta_{\text{placebo}1}$ to differ from zero. Further, because PKAN types may differ in response, we will test for an **interaction effect between PKAN type and treatment** averaged over dose levels as $CoASY_{ijt} = \beta_0 + \beta_1 I(aPKAN \text{ type}) + \beta_2 I(time = post) + \beta_{12} I(aPKAN)I(post) + b_i$, where indicator variables represent active vs placebo, atypical PKAN vs classic, and β_{12} is the coefficient for their interaction. 50% of participants are expected to have aPKAN.

At six months, we expect CoASY mRNA expression levels to have decreased somewhat, and that the group with the highest dose will show the lowest expression. In addition to repeating the comparisons outlined for initiation of treatment above, we will test $\beta_{\text{low}1} > \beta_{\text{mid}1} > \beta_{\text{high}1} > \beta_{\text{placebo}1}$.

As a final step, we will develop a longitudinal model to characterize CoASY mRNA expression profiles over the entire 24-month study period. We plan to use a mixed effects model with random intercept and slope to account for correlation between measurements and to allow individuals to vary from the group mean. We will explore a number of possible parameterizations of the time effect, including fractional polynomials and splines. We will allow for different trajectories by (a) dose group and (b) PKAN type in separate models with a group x time interaction. This model will take the general form $CoASY_{ij} = \beta_0 + \beta_1 t_{ij} + \beta'_2 group + \beta_3 t_{ij} \times group + b_{1i} + b_{2i} t_{ij}$, where t_{ij} represents time on treatment in months (including partial months as decimals) and group indicates dose group or PKAN type, depending on the model.

c. Statistical plan for exploratory aim

Sample Size and Statistical Power Issues

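### A participant under 5 who qualifies by genotype alone and has no motor symptoms is typed atypical by default, so participants of undetermined type enter the atypical side of the two by-type CoASY analyses

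*Combined protocol and SAP*

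**What the plan says.** **Typing (section 7.a, repeated in the synopsis).** "Classic PKAN participants are defined as those with onset of motor symptoms before age 5", with a further condition on lost ambulation that applies only to those over 10 at enrolment. Then: "Atypical PKAN participants are defined as all other PKAN participants who don't meet classic disease criteria". The planned size is stated as "Goal is n=30 atypical participants", with the same number for classic.

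**Eligibility (section 7.b).** The age criterion reads "Be between age 3 months to age 89 years at the time of screening". Diagnostic route (a) is "genetic testing confirming 2 pathogenic or likely pathogenic mutations" and asks for nothing clinical. Routes (b) and (c) add typical examination and MRI findings. Route (d) is to "be a symptomatic sibling of a proband subject meeting a, b, or c".

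**Use of the label.** Type stratifies the randomisation lists (section 10.e) and is a covariate in the day-3 CoASY model (section 10.b). Section 10.b also plans a test for an "interaction effect between PKAN type and treatment" and a longitudinal model with separate trajectories by type over 24 months. The synopsis repeats these analyses.

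**Background (section 4.a).** Classic disease is said to begin in the first few years of life. Of the other form it says: "Those individuals who have disease onset later in life tend to have less severe manifestations".

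**The concern.** The two definitions treat not yet having had motor onset before 5 as if it were the same as not having it. For a participant aged 5 or over the distinction is empty. For a participant under 5 it is not: the event that defines classic disease may still occur. The protocol deals with the equivalent problem for ambulation by applying that condition only to those over 10 at enrolment, but has no matching rule for onset. There is no undetermined category and no statement of which label the models use if motor symptoms begin on study.

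At stake is the interpretation of two secondary biomarker analyses. The type-by-treatment test is there because response may differ by disease type. A child whose type cannot yet be known tells us nothing reliable about that difference, yet the rule counts the child on the atypical side.

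**Working it through.** **1. Apply the rules to one case.** Take a child of 2 years with two pathogenic mutations and no motor symptoms.

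- Age criterion (7.b): met.
- Diagnostic criterion (7.b): met by route (a). No listed exclusion concerns absence of symptoms.
- Classic (7.a): not met, because there has been no motor onset.
- Atypical (7.a): met, as the residual class.
- Motor onset before 5: still possible for about three years.

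The same holds for any participant from 3 months to under 5 years who enters by route (a) without motor symptoms.

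**2. Follow the label (10.b, 10.e).**

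| Use | Effect of the default label |
|---|---|
| Randomisation stratum | None on validity: fixed before allocation |
| Covariate in the day-3 dose contrast | None on validity: a baseline covariate |
| Primary safety and tolerability comparison | None: made by arm, not by type |
| Type-by-treatment test | Undetermined participants counted as atypical |
| By-type 24-month model | Undetermined participants counted as atypical |

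**3. Size of the dilution.** The plan gives no figure for a by-type difference, so there is none to reproduce. Inputs: 30 planned atypical participants (7.a); k of them in fact respond as classic (assumed). Let D be the true type difference in CoASY response, and assume that the classic group is otherwise correctly typed and that the k children are spread over the arms like the rest. The labelled atypical mean is then a mixture, and

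estimated difference = D × (1 - k/30).

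- k = 0: no loss
- k = 1: 1 - 1/30 = 0.967, a loss of 3%
- k = 3: 1 - 3/30 = 0.900, a loss of 10%

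**4. Price of leaving them out.** With 30 classic and 30 - k atypical participants, the standard error of the type difference grows by √[(1/30 + 1/(30 - k)) / (2/30)].

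- k = 1: √1.0172 = 1.009, so 0.9% wider
- k = 3: √1.0556 = 1.027, so 2.7% wider

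**5. Illustration of power for k = 3.** Assumptions: 45 active participants, half of each type (22.5 per type); SD of change √2 × SD; two-sided alpha 0.10, which the plan states for the day-3 contrast; normal approximation. D is set to 0.54 dCt (17.39 - 16.85, the classic-versus-control gap in section 10.a) and to half of that. D is purely illustrative, since the documents report no CoASY values for atypical participants.

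For SD 0.48 and D = 0.54, the standard error is √2 × 0.48 × √(2/22.5) = 0.202.

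- No such children: Φ(0.54/0.202 - 1.645) = 85%
- Three left in: D becomes 0.486, and power is 78%
- Three left out (22.5 versus 20.25): the standard error is 0.208, and power is 83%

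| SD | D | None | 3 left in | 3 left out |
|---|---|---|---|---|
| 0.39 | 0.54 | 95% | 91% | 94% |
| 0.39 | 0.27 | 50% | 43% | 48% |
| 0.48 | 0.54 | 85% | 78% | 83% |
| 0.48 | 0.27 | 38% | 33% | 37% |

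Under these assumptions, leaving the children out recovers most of what keeping them in loses.

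**The case against.** The strongest reply is that a stratification factor must rest on what is known at enrolment, that the residual class is a clear rule, and that the analyses affected are secondary ones on a biomarker the protocol itself calls exploratory. The number of such children could be nil. All of that stands, and it limits the point to the two by-type analyses.

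The dilution formula is also open to challenge. The classic group may not be pure: a child of 10 or younger with onset before 5 is typed classic before the ambulation condition can be judged. The only CoASY data described in the sample size section are from 8 classic children and 6 controls, so neither the size nor the direction of a type difference is established. If presymptomatic infants differ from both groups, for example through age, the bias need not be towards zero. Age is planned only as a covariate in secondary analyses (10.d).

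Some stronger readings are tempting, but the documents do not support them:

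- *That randomisation is compromised.* The label is set before allocation, so the arms remain comparable.
- *That these children are put into a late-onset stratum.* Atypical is formally everyone else. It already includes someone over 10 with onset before 5 who kept walking past 10.
- *That the protocol declares the type comparison essential.* Section 7.c uses that word for including adults with limited decisional impairment. It does not rank the by-type analysis.

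What the reply does not answer is that a rule suited to stratification is carried unchanged into analyses meant to compare disease types.

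**Conclusion.** The gap follows from the definitions alone. A participant under 5 without motor symptoms, admitted by genotype, is counted as atypical while still able to become classic, and nothing in the plan removes such participants from the type-by-treatment test or the by-type longitudinal model. The active-versus-placebo contrast and the primary safety results are not affected.

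The size is unknown. With one to three such children among 30, a true type difference would lose 3% to 10%, provided that they respond as classic and that the classic group is otherwise correctly typed. Neither condition can be checked from the documents, k may be zero, and the direction is uncertain if presymptomatic infants form a third pattern. This is a modest correction to secondary analyses, worth making because it is cheap and is best settled before unblinding.

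**What to change.** In section 10.b and the matching synopsis text:

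1. Keep the randomisation stratum as assigned. Keep these children in the safety analysis and in the main CoASY dose contrast.
2. Define an analysis label 'undetermined' for participants under 5 with no motor symptoms at enrolment.
3. Leave that group out of the type-by-treatment test and the by-type 24-month model, and report how many they are.
4. Repeat both analyses with the as-stratified label as a sensitivity analysis.

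Retyping by motor onset seen during the study should be descriptive at most. Onset is observed after randomisation and could be influenced by treatment, and it may be unresolved at study end: a child entering at 3 months is about 2 years old after 24 months of treatment.

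The cost is a change of SAP wording and a few participants fewer in the by-type comparisons: a standard error about 1% wider for one child and 3% wider for three. Eligibility, allocation and treatment do not change.

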The secondary objective of this study is to assess the pharmacodynamic profile of an exploratory, 'proof-of-concept' molecular biomarker (CoASY mRNA expression) in response to the study product.

3. The secondary hypothesis is that CoASY is an inducible enzyme that will respond rapidly to exogenous substrate (4'-PPT) and subsequently decline in activity as a result of excess substrate and feedback inhibition; and that these changes will be detectable in peripheral CoASY mRNA expression levels. We anticipate that:

- CoASY mRNA expression levels will initially rise in all 4'-PPT-treated participants after 3 days ±2 days of treatment compared with placebo-treated participants; and
- CoASY mRNA expression levels will subsequently decline in all participants after completing treatment with 4'-PPT treatment, consistent with secondary down-regulation of CoASY activity in the presence of excess substrate, (i.e. feedback inhibition) and there will be no difference in CoASY mRNA expression between groups at 18-24 months.

The secondary endpoint is CoASY mRNA expression levels measured at 8 time points in the Primary Cohort and up to 6 timepoints in the Open-label Cohort.

In addition, in a third exploratory aim, with the goal of informing future studies of 4'-PPT or other compounds, we will assess the feasibility of applying a latent growth curve (LGC) approach to natural

history data collected before and during an intervention to capture a disease-modifying effect. The natural history data is being collected under a separate IRB-approved protocol eIRB 10832.

4. Background

a. PKAN is an ultra-rare inborn error of metabolism that disproportionately affects children and causes severe disability

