from PKAN patients compared to controls, mirroring the findings in the murine model. These transcriptional and functional differences are robust, yet they seem to be tolerated by these cell types both *in vitro* and *in vivo*. This phenomenon is not surprising, given that most cells in the human body, including most cells in brain, seem to tolerate a defect in *PANK2* without significant impairment. The basis for this selective vulnerability is not yet fully understood. We have not yet analyzed iron and dopamine mRNA expression biomarkers in human cells; however, we suspect that iron analytes will prove to be influenced more by systemic iron status rather than disease state.

e. The study product ameliorates the deficits in the mouse model and in cultured human cells.

Single gene disorders of intermediary metabolism offer the most direct path to rational therapeutics. By bypassing the enzyme block, alternate substrates can resolve the primary defect near to its source and avert development of downstream sequelae. In the Pank2 KO mice, we have found that oral administration of the study product, 4'-phosphopantethine (4'-PPT), normalizes CoA-, iron-, and dopamine-related changes in brain. Fourteen-day feeding of 4'-PPT leads to a dose-responsive correction in the expression of all perturbed biomarker genes, suggesting that 4'-PPT normalizes CoA metabolism in the KO mouse. The secondary correction of iron and dopamine defects resulting from normalizing CoA metabolism is strong evidence that these perturbations arise as a direct sequela of the CoA defect and, importantly, that they are reversible at the level of both transcript and cellular metabolism. When the study product is withdrawn, the levels return to the aberrant pre-treatment levels. Importantly, the study product also corrects the mitochondrial functional defects observed in transformed fibroblasts from PKAN patients.

These pre-clinical data provide a compelling rationale for advancing 4'-PPT to clinical studies. Further, because the study product is identical to a naturally-occurring product of intermediary metabolism and will be used in very low doses intended to mimic physiologic levels, we can justify the first clinical studies being in the target population, including vulnerable child populations.

5. Study Design

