This will be a single site, phase 2, safety and tolerability trial of 4'-phosphopantetheine (4'-PPT), a downstream product of intermediary metabolism in children and adults with PKAN, a inborn error of vitamin B5 metabolism. An initial 6-month, dose-ranging, parallel-group, randomized, double-blind, placebo-controlled phase will be followed by an 18-month, single-dose, open-label phase. There will be up to 2 months for screening and up to 2 months for follow up for up to a total of 28 months participation for this Primary Cohort. During the double-blind phase, participants in the Primary Cohort will be assigned randomly to one of three dose groups or placebo, with a 1:1:1:1 distribution. Once we meet our enrollment target for the Primary Cohort, we will shift additional enrollment directly into a single-dose open-label arm that will last up to 18 months per participant including up to 2 months for screening and up to 2 months for follow up. Our primary hypothesis is that there will be no clinically significant difference in safety or tolerability profiles between active and placebo groups during six months of double-blind parallel-group study, nor between dose groups over up to 18 months of treatment with 4'-PPT. Safety measures will include treatment-emergent adverse events collected at 10 time points and abnormalities on standard laboratory tests collected at 9 time points over 25 months (including follow up) for Primary Cohort participants. For the Open-label Cohort, treatment-emergent adverse events will be collected at up to 7 time points and safety labs at up to 6 time points over up to 20 months (including follow up). Participants will be stratified by PKAN type: classic or atypical, to ensure approximately equal distribution in each arm.

As a secondary, “proof of concept” aim, we will assess the pharmacodynamic profile of CoASY mRNA expression in the peripheral blood of participants receiving 4'-PPT or placebo. We will measure CoASY mRNA expression at 8 time points for the Primary Cohort and at up to 6 timepoints for the Open-label Cohort to examine four secondary hypotheses:

- a. **CoASY mRNA expression levels will rise in all 4'-PPT-treated participants after 1 month of treatment** compared with placebo-treated participants.

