- b. There will be **no difference in CoASY mRNA expression between 4'-PPT dose groups after 1 month of treatment**. Statistical tests will fail to reject the null and the magnitude of the difference will be small compared to the one-month change.
- c. **After 6 months of treatment, CoASY mRNA expression levels will vary inversely with 4'-PPT dose**, and
- d. There will be **no difference between initial dose groups [placebo/active] after up to 18 months on the same active dose**, consistent with down-regulation of CoASY activity in the presence of excess substrate, (i.e. feedback inhibition).

6. Study Product

The study product is 4'-phosphopantetheine (4'-PPT) formulated in a fruit-flavored syrup suitable for administration by mouth or via G-tube. Several factors contribute to the prediction that 4'-PPT is of very low toxic potential^[9]. First, it is a synthetic version of a naturally-occurring product of intermediary metabolism in the vitamin B5 pathway [See Figure 1]. Second, the compound has shown no evidence of toxicity when given to mice in doses far in excess of those used in this trial. Third and perhaps most important, it will be used in very low doses intended to mimic physiologic levels: all doses employed in the study are based on a range tested in the mouse model as the ‘minimum effective’, rather than the more usual ‘maximum tolerated’ doses. Although derived from mouse studies, the dose range to be used in this trial turns out to be remarkably close to the molar equivalent of the Recommended Daily Allowance (RDA) of pantothenate, the upstream vitamin the study product aims to replace, which itself shows little toxicity even in doses far in excess of the RDA, with no upper limit established by the Institute of Medicine^[10].

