The Baseline visit will be conducted by phone. Concomitant medications, adverse events, study product dosing and administration, and instructions for the visit 1 and 2 blood draws will be reviewed with the participant. The timing of the first product administration will be mutually confirmed between the participant and the study staff; this will determine the study schedule going forward. Participants will be instructed in the logistics and importance of getting safety and biomarker labs drawn on schedule, completing the dosing diary, documenting the timing and nature of any adverse events, and returning left-over study product at the end of each dosing period as each new batch of product is received.

c. Follow-up visits

Follow-up visits will be conducted by phone, with the timing and activities as detailed in the Schedule of Activities table on p. 23-26. Study product, blood draw kits and pre-paid return shipping materials for return of study product will be sent to the participant at intervals throughout the study. The timing and frequency of study product shipments will be dictated not only by the study schedule but also likely by FDA feedback on stability data from the ongoing shelf-life studies. Participants will always receive more study product than needed to supply them to the next shipment date or study visit date to ensure there is no interruption in dosing due to shipment delays. Study staff will arrange for the blood draws and height / weight measurement with a CLIA-certified lab local to the participant's home as per the Schedule of Activities. Participants will return left-over study product to the study site using pre-paid shipping materials at the end of each dosing interval as new product is received.

d. End-of-study visit

The Primary Cohort participants will take their final dose of study product at Month 24 visit, ideally on the same day as the Month 24 scheduled blood draw for safety and biomarker labs. A final study visit will take place at Month 25 (+ 1 month window allowed for final follow up); at a minimum, this will include AE and Concomitant Medications assessment; safety and / or biomarker labs may be added at investigator discretion, for example if any safety lab value at the Month 24 visit shows clinically significant abnormalities or if a sample was compromised.

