An unscheduled visit may be conducted at investigators' discretion at any point in the study in response to an adverse event or other clinically-significant event. Such a visit will always include assessment of adverse events and concomitant medications; safety labs and biomarker labs may be added at the investigator's discretion.

eIRB 18782 CoA-Z in PKAN (NIH)

Schedule of Activities for Primary Cohort Participants

Procedures Primary Cohort	Screening#	Baseline#	Visit 1	Visit 2	Visit 3	Visit 4	Visit 5	Visit 6	Visit 7	Visit 8	Visit 9	Visit 10	Visit 11
	Month -2	Month 0	Month 0 + 3 days +/- 2d	Month 1 +/- 5d	Month 3 +/- 5d	Month 6 -10 to 0d	Month 6 + 3 days +/- 2d	Month 7 +/- 5d	Month 9 +/- 5d	Month 12 +/- 5d	Month 18 +/- 5d	Month 24 +/- 5d	Month 25 + 1 month/- 5d
Informed Consent	X												
Demographics	X												
Medical history / Confirmation of PKAN diagnosis	X												
Randomization	X												
Complete metabolic profile ^{A,B}	X			X	X	X		X	X	X	X	X	
CBC with differential ^B	X			X	X	X		X	X	X	X	X	
Biomarker labs ^B	X		X	X		X	X			X			X
Height / Weight ^C	X					X				X	X	X	
Study product reconciliation				X	X	X		X	X	X	X	X	
Concomitant Medications Log	X	X		X	X	X		X	X	X	X	X	X
Evaluate for Adverse Events		X		X	X	X		X	X	X	X	X	X

eIRB 18782 CoA-Z in PKAN (NIH)

A = Standard CMP includes Na⁺, K⁺, Cl⁻, CO₂, BUN, Creat, Ca²⁺, Glu, Alb, T. Protein, Alk Phos, T. Bili, AST, ALT. CK may be ordered separately.

B= If a technical error occurs drawing, running, or shipping a lab, it may need to be repeated. Minor variations in safety lab components allowable at PI discretion.

C= Height and weight will be measured more frequently at the PI's discretion for children based on age and apparent growth rate

An unscheduled visit may be conducted at investigators' discretion at any point in the study in response to AE or other clinically-significant event. Such a visit will include AE assessment and concomitant medications assessment. Safety labs and biomarker labs may be added at investigator discretion. For subjects who are hospitalized, were recently discharged, or are too sick to leave home for safety labs, it is acceptable to use clinical labs collected up to 14 days before or after the study window.

eIRB 18782 CoA-Z in PKAN (NIH)

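### The Primary Cohort schedule marks 7 CoASY draws, none at Month 18 or 24 and one after the final dose, while the text states 8 and schedules a Month 24 draw

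*Combined protocol and SAP*

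**What the plan says.** **Number of draws.** The synopsis (Secondary Outcomes) describes "CoASY mRNA expression levels measured at 8 time points in the Primary Cohort". Section 3 repeats the figure when it defines the secondary endpoint, and Section 5 says "We will measure CoASY mRNA expression at 8 time points for the Primary Cohort". None of these places lists the eight visits.

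**End of treatment.** Section 8.d has Primary Cohort participants take their last dose at the Month 24 visit, "ideally on the same day as the Month 24 scheduled blood draw for safety and biomarker labs". At the Month 25 visit the required items are adverse events and concomitant medications. Safety and biomarker labs may be added there at the investigator's discretion.

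**Schedule.** The biomarker row of the Schedule of Activities for Primary Cohort Participants is marked at Screening, Month 0+3 days, Month 1, Month 6, Month 6+3 days, Month 12 and Month 25. Months 18 and 24 are blank. Section 8.c refers staff to this table for the timing and content of follow-up visits.

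**What the late samples are for.** Section 5, hypothesis d, predicts "no difference between initial dose groups [placebo/active] after up to 18 months on the same active dose" and attributes this to feedback inhibition with excess substrate present. Section 3 places the same comparison at 18-24 months. Section 10.b plans a longitudinal model over 24 months with time on treatment as its time axis.

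**Withdrawal.** On the knock-out mouse, Section 4.e reports: "When the study product is withdrawn, the levels return to the aberrant pre-treatment levels".

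**The concern.** The table disagrees with the text in three ways: the total number of draws, the absence of a Month 24 draw, and a routine rather than discretionary draw at Month 25. This is more than clerical. The trial is run from one site, which ships the blood-draw kits, so one reading of the row would apply to every Primary Cohort participant.

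Under the table, the late hypothesis has no on-product sample in the window that Section 3 names. The only later value comes after the final dose. Untreated PKAN is the low-expression state (Section 10.a: mean dCt 17.39 against 16.85 in controls, with higher dCt meaning lower activity). A drift back towards that state after stopping would lower expression in all groups. The plan predicts the same pattern, late decline with no difference between groups, as the result of feedback inhibition on product. A Month 25 sample could not separate the two explanations.

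**Working it through.** **1. Reproduce the stated counts.** Marks were counted by visit column, 13 columns in the Primary Cohort table and 9 in the Open-label table, and compared with the synopsis and Section 5.

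| Row | Stated | Marks |
|---|---|---|
| Primary, safety labs (CMP, CBC) | 9 | 9 |
| Primary, adverse events | 10 | 10 |
| Primary, biomarker | 8 | **7** |
| Open-label, safety labs | 6 | 6 |
| Open-label, adverse events | 7 | 7 |
| Open-label, biomarker | 6 | 6 |

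Only the Primary Cohort biomarker row fails. It has its full 13 cells.

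**2. Compare the two schedules.** The Open-label table draws biomarkers at its last on-product visit (Month 18) and not at follow-up (Month 19). The Primary Cohort row does the reverse: nothing at Month 24, a mark at Month 25.

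**3. Which changes give 8?**
- Keep all marks and add Month 24: 7 + 1 = 8. This agrees with Section 8.d on Month 24 but leaves Month 25 routine.
- Drop Month 25, add Months 18 and 24: 7 - 1 + 2 = 8. This agrees with Section 8.d on both visits.
- Add Month 18 only: 7 + 1 = 8, but still no Month 24 draw, against Section 8.d.
- Move Month 25 to Month 24: 7 - 1 + 1 = 7. The count still fails.

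The documents do not say which set is intended. Any set consistent with Section 8.d includes Month 24.

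**4. On-product follow-up under the table.** The open-label dose starts at Month 6 and the last on-product sample is at Month 12. That is 12 - 6 = 6 months on the common dose, against the 24 - 6 = 18 months in hypothesis d. For CoASY alone, the on-product period without a sample is 24 - 12 = 12 of 24 months.

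**5. How far off product is the Month 25 sample?** The visit window is -5 days to +1 month, and one month is 365.25/12 = 30.4 days. With the last dose at nominal Month 24:
- earliest: 30.4 - 5 = 25.4 days;
- latest: 30.4 + 30.4 = 60.9 days (before rounding, 60.875).

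Allowing the ±5-day window at Month 24 as well, the range is about 20 to 66 days.

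**6. What is not touched.** The early contrast uses the baseline and 3-day samples, both marked in the row. The 85-95% power statement in Section 10.a concerns that contrast. Safety labs and adverse events are marked through Month 24.

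**The case against.** **The table may have been misread.** It comes from a PDF and this is the only row that fails. A full set of cells does not rule out a lost or shifted mark. This stands as a caveat, and the source table should be checked first. It does not dispose of the point. One shifted mark leaves the count at 7. One lost mark at Month 24 would restore the count and the draw, but the routine Month 25 mark would still disagree with Section 8.d.

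**The text already provides the sample.** Section 8.d schedules the Month 24 draw, Section 3 sets the comparison at 18-24 months, and no analysis section assigns hypothesis d to Month 25. This is correct. A reader might infer that the trial was designed without an end-of-treatment CoASY sample; the documents do not support that. They show two conflicting instructions, and the loss occurs only if the table is followed.

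**Reversal on withdrawal is not established in patients.** Section 4.e describes mice and gives no human washout time for CoASY in blood. A reader might infer that groups would agree at Month 25 because all are off product. The documents support only that this could happen. Since all groups receive the same dose from Month 6, agreement at Month 24 would not by itself prove feedback inhibition either. An on-product sample removes one competing explanation, not all.

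**An off-product sample might be intended.** Section 3 speaks of a decline after treatment is completed. But the mechanism it gives requires substrate to be present, and the same sentence compares groups at 18-24 months.

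**The endpoint is secondary.** True. The protocol calls the biomarker exploratory and proof of concept, which limits the weight of the point.

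**Conclusion.** The inconsistency is real: 7 marked draws against 8 stated, a Month 24 draw that is in the text but not in the table, and a Month 25 draw that is routine in the table but discretionary in the text. If the table governs, on-product CoASY data end at Month 12. The 18-24 month comparison and the later half of the 24-month model then have no on-product sample, or lean on one taken about 25 to 61 days after the last dose.

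This rests on the row having been read correctly and on staff following the table rather than Section 8.d. That a Month 25 value would mislead is a possibility drawn from mouse data, not a demonstrated effect in patients. The point should be corrected, but it does not affect the primary safety and tolerability endpoints, the 3-day contrast or its power statement.

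**What to change.** 1. Check the biomarker row against the source table.
2. Reconcile the synopsis, Sections 3, 5 and 8.d, and the Schedule of Activities. List the eight biomarker visits by name, including the Month 24 draw that Section 8.d already schedules, and state whether Month 25 is routine or discretionary.
3. In Section 10.b and the synopsis, name the on-product visit or visits used for the 18-24 month comparison.
4. In that comparison and in the longitudinal model, exclude only samples taken after the participant's final dose, and report those separately. Keep the pre-treatment baseline and placebo-phase samples. A blanket restriction to on-product samples would remove the baseline and every placebo-group value through Month 6, which the planned models need.

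The cost is one corrected table row and a few sentences of analysis text. Safety blood is already drawn at Months 18 and 24, so no extra visit or venipuncture is needed, only the biomarker sample with its shipping and assay. A Month 24 sample that is not collected cannot be recovered later.
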